### 8. ADVERSE EVENT REPORTING

#### 8.1. Adverse Events

All observed or volunteered AEs regardless of treatment group or suspected causal relationship to the investigational product(s) will be reported as described in the following sections.

For all AEs, the investigator must pursue and obtain information adequate both to determine the outcome of the AE and to assess whether it meets the criteria for classification as an SAE requiring immediate notification to Pfizer or its designated representative. For all AEs, sufficient information should be obtained by the investigator to determine the causality of the AE. The investigator is required to assess causality. Follow-up by the investigator may be required until the event or its sequela resolve or stabilize at a level acceptable to the investigator, and Pfizer concurs with that assessment.

As part of ongoing safety reviews conducted by the sponsor, any non-serious AEs that are determined by the sponsor to be serious will be reported by the sponsor as an SAE. To assist in the determination of case seriousness, further information may be requested from the investigator to provide clarity and understanding of the event in the context of the clinical study.

# 8.2. Reporting Period

For SAEs, the active reporting period to Pfizer or its designated representative begins from the time that the patient provides informed consent, which is obtained prior to the patient's participation in the study, ie, prior to undergoing any study-related procedure and/or receiving investigational product, through 98 calendar days from first administration of the investigational product, or up to 60 days after last administration of investigational product, whichever is later. SAEs occurring to a patient after the active reporting period has ended should be reported to the sponsor if the investigator becomes aware of them; at a minimum,

all SAEs that the investigator believes have at least a reasonable possibility of being related to investigational product are to be reported to the sponsor.

If a serious adverse event occurs after informed consent is signed and before investigational product is administered, this information will be reported on a Serious Adverse Event Form and will be recorded in the safety database.

AEs (non-serious) should be recorded on the CRF from the time the patient has taken at least 1 dose of study treatment through 28 days after the last treatment administration or until all drug related toxicities have resolved, whichever is later. However, late immune-related DLTs that are not SAEs need to be collected consistent with Section 3.2.1.

If a patient begins a new anticancer therapy, the AE reporting period for non-serious AEs ends at the time the new treatment is started. Death must be reported if it occurs during the SAE reporting period after the last dose of investigational product, irrespective of any intervening treatment.

### 8.3. Definition of an Adverse Event

An AE is any untoward medical occurrence in a clinical investigation patient administered a product or medical device; the event need not necessarily have a causal relationship with the treatment or usage. Examples of AEs include but are not limited to:

- Abnormal test findings;
- Clinically significant symptoms and signs;
- Changes in physical examination findings;
- Hypersensitivity;
- Drug abuse;
- Drug dependency.

Additionally, they may include the signs or symptoms resulting from:

- Drug overdose;
- Drug withdrawal;
- Drug misuse;
- Drug interactions;
- Extravasations;
- Exposure during pregnancy (EDP);

- Exposure via breastfeeding;
- Medication error;
- Occupational exposure.

Worsening of signs and symptoms of the malignancy under study should be reported as AEs in the appropriate section of the CRF. Disease progression assessed by measurement of malignant lesions on radiographs or other methods should not be reported as AEs.

#### 8.4. Medication Errors

Medication errors may result, in this study, from the administration or consumption of the wrong product, by the wrong patient, at the wrong time, or at the wrong dosage strength. Such medication errors occurring to a study participant are to be captured on the medication error CRF which is a specific version of the AE page, and on the SAE form when appropriate. In the event of medication dosing error, the sponsor should be notified immediately.

Medication errors are reportable irrespective of the presence of an associated AE/SAE, including:

- Medication errors involving patient exposure to the investigational product;
- Potential medication errors or uses outside of what is foreseen in the protocol that do or do not involve the participating patient.

Whether or not the medication error is accompanied by an AE, as determined by the investigator, the medication error is captured on the medication error version of the AE page and, if applicable, any associated AEs are captured on an adverse event (AE) CRF page.

# 8.5. Abnormal Test Findings

The criteria for determining whether an abnormal objective test finding should be reported as an AE are as follows:

- Test result is associated with accompanying symptoms; and/or
- Test result requires additional diagnostic testing or medical/surgical intervention; and/or
- Test result leads to a change in study dosing or discontinuation from the study, significant additional concomitant drug treatment, or other therapy; and/or
- Test result is considered to be an AE by the investigator or sponsor.

Merely repeating an abnormal test, in the absence of any of the above conditions, does not constitute an AE. Any abnormal test result that is determined to be an error does not require reporting as an AE.

#### **8.6. Serious Adverse Events**

A serious adverse event is any untoward medical occurrence at any dose that:

- Results in death;
- Is life-threatening (immediate risk of death);
- Requires inpatient hospitalization or prolongation of existing hospitalization;
- Results in persistent or significant disability/incapacity (substantial disruption of the ability to conduct normal life functions);
- Results in congenital anomaly/birth defect;
- Progression of the malignancy under study (including signs and symptoms of progression) should not be reported as an SAE unless the outcome is fatal within the safety reporting period. Hospitalization due to signs and symptoms of disease progression should not be reported as an SAE. If the malignancy has a fatal outcome during the study or within the safety reporting period, then the event leading to death must be recorded as an AE and as an SAE with CTCAE Grade 5 (see Section 8.8 on Severity Assessment).

Medical and scientific judgment is exercised in determining whether an event is an important medical event. An important medical event may not be immediately life-threatening and/or result in death or hospitalization. However, if it is determined that the event may jeopardize the patient or may require intervention to prevent one of the other AE outcomes, the important medical event should be reported as serious.

Examples of such events are intensive treatment in an emergency room or at home for allergic bronchospasm; blood dyscrasias or convulsions that do not result in hospitalization; or development of drug dependency or drug abuse.

### **8.6.1. Protocol Specified Serious Adverse Events**

There are no protocol-specified SAEs in this study. All SAEs will be reported by the investigator as described in previous sections and will be handled as SAEs in the safety database (see Section 8.14.1 on Serious Adverse Event Reporting Requirements).

### 8.6.2. Potential Cases of Drug Induced Liver Injury

Abnormal values in aspartate aminotransferase (AST) and/or alanine aminotransferase (ALT) levels concurrent with abnormal elevations in total bilirubin level that meet the criteria outlined below in the absence of other causes of liver injury are considered potential cases of drug-induced liver injury (potential Hy's law cases) and should always be considered important medical events.

The threshold of laboratory abnormalities for a potential case of drug-induced liver injury depends on the patient's individual baseline values and underlying conditions. Patients who present with the following laboratory abnormalities should be evaluated further to definitively determine the etiology of the abnormal laboratory values:

- Patients with AST or ALT and total bilirubin baseline values within the normal range who subsequently present with AST or ALT values  $\geq 3$  times the upper limit of normal (x ULN) concurrent with a total bilirubin value  $\geq 2$  x ULN with no evidence of hemolysis and an alkaline phosphatase value  $\leq 2$  x ULN or not available;
- For patients with preexisting ALT **OR** AST **OR** total bilirubin values above the ULN, the following threshold values should be used in the definition mentioned above:
  - For patients with preexisting AST or ALT baseline values above the normal range, AST or ALT value  $\ge 2$  times the baseline values and  $\ge 3$  x ULN, or  $\ge 8$  x ULN (whichever is smaller).

#### Concurrent with

• For patients with pre-existing values of total bilirubin above the normal range: Total bilirubin level increased from baseline by an amount of at least 1 x ULN **or** if the value reaches  $\geq$ 3 x ULN (whichever is smaller).

The patient should return to the investigational site and be evaluated as soon as possible, preferably within 48 hours from awareness of the abnormal results. This evaluation should include laboratory tests, detailed history, and physical assessment. The possibility of hepatic neoplasia (primary or secondary) should be considered. In addition to repeating measurements of AST and ALT, laboratory tests should include albumin, creatine kinase, total bilirubin, direct and indirect bilirubin, gamma-glutamyl transferase, prothrombin time (PT)/international normalized ratio (INR), and alkaline phosphatase. A detailed history, including relevant information, such as review of ethanol, acetaminophen, recreational drug and supplement consumption, family history, occupational exposure, sexual history, travel history, history of contact with a jaundiced person, surgery, blood transfusion, history of liver or allergic disease, and work exposure, should be collected. Further testing for acute hepatitis A, B, or C infection and liver imaging (eg, biliary tract) may be warranted. All cases confirmed on repeat testing as meeting the laboratory criteria defined above, with no other cause for liver function test (LFT) abnormalities identified at the time, should be considered potential Hy's Law cases irrespective of availability of all the results of the investigations performed to determine etiology of the abnormal LFTs. Such potential Hy's law cases should be reported as SAEs.

### 8.7. Hospitalization

Hospitalization is defined as any initial admission (even less than 24 hours) in a hospital or equivalent healthcare facility or any prolongation of an existing admission. Admission also includes transfer within the hospital to an acute/intensive care unit (eg, from the psychiatric wing to a medical floor, medical floor to a coronary care unit, or neurological floor to a tuberculosis unit). An emergency room visit does not necessarily constitute a hospitalization;

however, the event leading to the emergency room visit should be assessed for medical importance.

Hospitalization does not include the following:

- Rehabilitation facilities:
- Hospice facilities;
- Respite care (eg, caregiver relief);
- Skilled nursing facilities;
- Nursing homes;
- Same-day surgeries (as outpatient/same day/ambulatory procedures).

Hospitalization or prolongation of hospitalization in the absence of a precipitating, clinical AE is not in itself an SAE. Examples include:

- Admission for treatment of a preexisting condition not associated with the development of a new AE or with a worsening of the preexisting condition (eg, for workup of persistent pre-treatment laboratory abnormality);
- Social admission (eg, patient has no place to sleep);
- Administrative admission (eg, for yearly physical examination);
- Protocol-specified admission during a study (eg, for a procedure required by the study protocol);
- Optional admission not associated with a precipitating clinical AE (eg, for elective cosmetic surgery);
- Hospitalization for observation without a medical AE;
- Preplanned treatments or surgical procedures. These should be noted in the baseline documentation for the entire protocol and/or for the individual patient;
- Admission exclusively for the administration of blood products.

Diagnostic and therapeutic noninvasive and invasive procedures, such as surgery, should not be reported as AEs. However, the medical condition for which the procedure was performed should be reported if it meets the definition of an AE. For example, an acute appendicitis that begins during the AE reporting period should be reported as the AE, and the resulting appendectomy should be recorded as treatment of the AE.

### 8.8. Severity Assessment

GRADE	Clinical Description of Severity			
0	No Change from normal or reference range (This grade is not included in the Version 4.03 CTCAE document but may be used in certain circumstances.)			
1	MILD adverse event			
2	MODERATE adverse event			
3	SEVERE adverse event			
4	LIFE-THREATENING consequences; urgent intervention indicated			
5	DEATH RELATED TO adverse event			

Note the distinction between the severity and the seriousness of an AE. A severe event is not necessarily an SAE. For example headache may be severe (interferes significantly with the patient's usual function) but would not be classified as serious unless it met one of the criteria for SAEs listed above.

# 8.9. Causality Assessment

The investigator's assessment of causality must be provided for all AEs (serious and non-serious); the investigator must record the causal relationship in the CRF, as appropriate, and report such an assessment in accordance with the SAE reporting requirements if applicable. An investigator's causality assessment is the determination of whether there exists a reasonable possibility that the investigational product caused or contributed to an AE; generally the facts (evidence) or arguments to suggest a causal relationship should be provided. If the investigator does not know whether or not the investigational product caused the event, then the event will be handled as "related to investigational product" for reporting purposes, as defined by the sponsor (see Section 8.14 on Reporting Requirements). If the investigator's causality assessment is "unknown but not related to investigational product," this should be clearly documented on study records.

In addition, if the investigator determines that an SAE is associated with study procedures, the investigator must record this causal relationship in the source documents and CRF, as appropriate, and report such an assessment in accordance with the SAE reporting requirements, if applicable.

#### 8.10. Exposure During Pregnancy

For both unapproved/unlicensed products and for marketed products, an exposure during pregnancy occurs if:

1. A female becomes, or is found to be, pregnant either while receiving or having been exposed (eg, because of treatment or environmental exposure) to the investigational product; or the female becomes, or is found to be pregnant after discontinuing and/or being exposed to the investigational product;

An example of environmental exposure would be a case involving direct contact with a Pfizer product in a pregnant woman (eg, a nurse reports that she is pregnant and has been exposed to chemotherapeutic products).

2. A male has been exposed (eg, because of treatment or environmental exposure) to the investigational product prior to or around the time of conception and/or is exposed during his partner's pregnancy.

If a study patient or study patient's partner becomes or is found to be pregnant during the study patient's treatment with the investigational product, the investigator must submit this information to the Pfizer drug safety unit on a an SAE report form and an exposure during pregnancy (EDP supplemental form, regardless of whether an SAE has occurred. In addition, the investigator must submit information regarding environmental exposure to a Pfizer product in a pregnant woman (eg, a patient reports that she is pregnant and has been exposed to a cytotoxic product by inhalation or spillage) using the EDP supplemental form. This must be done irrespective of whether an AE has occurred and within 24 hours of awareness of the exposure. The information submitted should include the anticipated date of delivery (see below for information related to termination of pregnancy).

Follow-up is conducted to obtain general information on the pregnancy and its outcome for all EDP reports with an unknown outcome. The investigator will follow the pregnancy until completion or until pregnancy termination and notify Pfizer of the outcome as a follow-up to the initial EDP supplemental form. In the case of a live birth, the structural integrity of the neonate can be assessed at the time of birth. In the event of a termination, the reason(s) for the termination should be specified and, if clinically possible, the structural integrity of the terminated fetus should be assessed by gross visual inspection (unless pre-procedure test findings are conclusive for a congenital anomaly and the findings are reported).

If the outcome of the pregnancy meets the criteria for an SAE (ie, ectopic pregnancy, spontaneous abortion, intrauterine fetal demise, neonatal death, or congenital anomaly [in a live-born baby, a terminated fetus, an intrauterine fetal demise or a neonatal death]), the investigator should follow the procedures for reporting SAEs.

Additional information about pregnancy outcomes that are reported as SAEs follows:

- Spontaneous abortion includes miscarriage and missed abortion;
- Neonatal deaths that occur within 1 month of birth should be reported, without regard to causality, as SAEs. In addition, infant deaths after 1 month should be reported as SAEs when the investigator assesses the infant death as related or possibly related to exposure to the investigational product.

Additional information regarding the EDP may be requested by the investigator. Further follow-up of birth outcomes will be handled on a case-by-case basis (eg, follow-up on preterm infants to identify developmental delays). In the case of paternal exposure, the investigator will provide the study patient with the Pregnant Partner Release of Information Form to deliver to his partner. The investigator must document in the source documents that the patient was given the Pregnant Partner Release of Information Form to provide to his partner.

### 8.11. Occupational Exposure

An occupational exposure occurs when during the performance of job duties, a person (whether a healthcare professional or otherwise) gets in unplanned direct contact with the product, which may or may not lead to the occurrence of an AE.

An occupational exposure is reported to the drug safety unit within 24 hours of the Investigator's awareness, using the SAE Report form, regardless of whether there is an associated AE/SAE. Since the information does not pertain to a patient enrolled in the study, the information is not reported on a CRF; however a copy of the completed SAE Report form is maintained in the investigator site file.

# 8.12. Withdrawal Due to Adverse Events (See also Section 6.4 Patient Withdrawal)

Withdrawal due to AE should be distinguished from withdrawal due to other causes, according to the definition of AE noted earlier, and recorded on the appropriate AE CRF page.

When a patient withdraws because of an SAE, the SAE must be reported in accordance with the reporting requirements defined below.

# 8.13. Eliciting Adverse Event Information

The investigator is to report all directly observed AEs and all AEs spontaneously reported by the study patient. In addition, each study patient will be questioned about AEs.

#### 8.14. Reporting Requirements

Each AE is to be assessed to determine if it meets the criteria for SAEs. If an SAE occurs, expedited reporting will follow local and international regulations, as appropriate.

#### 8.14.1. Serious Adverse Event Reporting Requirements

If an SAE occurs, Pfizer is to be notified within 24 hours of investigator awareness of the event. In particular, if the SAE is fatal or life-threatening, notification to Pfizer must be made immediately, irrespective of the extent of available AE information. This time frame also applies to additional new information (follow-up) on previously forwarded SAE reports as well as to the initial and follow-up reporting of EDP, exposure via breastfeeding and occupational exposure cases.

In the rare event that the investigator does not become aware of the occurrence of an SAE immediately (eg, if an outpatient study patient initially seeks treatment elsewhere), the investigator is to report the event within 24 hours after learning of it and document the time of his or her first awareness of the AE.

For all SAEs, the investigator is obligated to pursue and provide information to Pfizer in accordance with the time frames for reporting specified above. In addition, an investigator may be requested by Pfizer to obtain specific additional follow-up information in an expedited fashion. This information collected for SAEs is more detailed than that captured on the AE CRF. In general, this will include a description of the AE in sufficient detail to

allow for a complete medical assessment of the case and independent determination of possible causality. Information on other possible causes of the event, such as concomitant medications, vaccines, and/or illnesses, must be provided. In the case of a patient death, a summary of available autopsy findings must be submitted as soon as possible to Pfizer or its designated representative.

# 8.14.2. Non-Serious Adverse Event Reporting Requirements

All AEs will be reported on the AE page(s) of the CRF. It should be noted that the form for collection of SAE information is not the same as the AE CRF. Where the same data are collected, the forms must be completed in a consistent manner. For example, the same AE term should be used on both forms. AEs should be reported using concise medical terminology on the CRFs as well as on the form for collection of SAE information.

# 8.14.3. Sponsor Reporting Requirements to Regulatory Authorities

AE reporting, including suspected unexpected serious adverse reactions, will be carried out in accordance with applicable local regulations.

### 9. DATA ANALYSIS/STATISTICAL METHODS

## 9.1. Analysis Sets

a. Safety analysis set.

The safety analysis set includes all enrolled patients who receive at least one dose of study medication.

b. Full analysis set.

The full analysis set includes all enrolled patients.

c. Per protocol analysis set (evaluable for MTD).

The per protocol analysis set includes all enrolled patients who receive at least one dose of study medication and who do not have major treatment deviations during first cycle. Patients with major treatment deviations in DLT observation period are not evaluable for the MTD assessment and will be replaced as needed to permit MTD estimation. Major treatment deviations include:

- Administration of less than 75% of the planned dose of PF-04518600 provided that the reduction is not due to toxicity attributable to PF-04518600.
- Administration of more than 150% of the planned dose of PF-04518600.
- d. PK analysis sets.

The PK parameter analysis population is defined as all enrolled patients treated who have sufficient information to estimate at least 1 of the PK parameters of interest.

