# 5.4.5.6.2. Part B Combination Therapy

Intrapatient dose reductions are not permitted during the combination therapy with PF-04518600 and utomilumab unless, in discussion with the sponsor, a dose combination level is deemed to be above the determined MTD for the combination.

Given the expected similarities of side effect profile and mechanism between the two co-stimulation monoclonal antibodies, both treatments must be interrupted or discontinued together. Patients will not be permitted to continue treatment with one agent, while the other agent is either interrupted or permanently discontinued. If infusion related reactions are observed following the administration of the first agent, administration of the second agent will be withheld until symptoms resolve (see Section 5.4.5.1 Infusion Reactions).

Treatment of irAEs should follow guidelines set forth in Table 4 in Section 5.4.5.4 Recommended dose modifications for any other drug-related toxicity are illustrated in Table 6.

Table 6. Treatment Interruptions/ Discontinuations for Drug Related Toxicity at Start of Subsequent Cycle

Toxicity	NCI CTCAE Severity Grade	Treatment Modifications
Hematologic abnormalities.	Grade 3	
 
Withhold until recovery to Grade 1 or better.
 
If toxicity does not resolve to Grade 1 or better within 4 weeks of last infusion, consider permanent discontinuation after consultation with the sponsor.
 
Upon the second occurrence of the same Grade 3 toxicity that does not resolve to Grade ≤1 by the next administration, treatment must be permanently discontinued.
 

	Grade 4	Permanent discontinuation.     Exceptions are:     Single laboratory values out of normal range that are unlikely related to investigational product (s) as assessed by the Investigator, do not have any clinical correlate, and resolve within 7 days with adequate medical management.
Infusion-related reaction.	Grade 1-4	• See Section 5.4.5.1 and Appendix 4.
Hypersensitivity reaction.	Grade 1-4	• See Section 5.4.5.2 and Appendix 4.

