### 9.2. Statistical Methods and Properties

### 9.2.1. Statistical Methods for Dose Escalation/De-Escalation

# 9.2.1.1. Part A Monotherapy

For the monotherapy portion of the study, a mTPI design  will be adopted for dose escalation and de-escalation determination. The mTPI design uses a Bayesian statistics framework and a beta-binomial hierarchical model with prior distribution of DLT set as a beta (0.75, 0.65) to compute the posterior probability of three dosing intervals that reflect the relative difference between the toxicity rate of each dose level to the target rate (pT=0.25, where pT is the target probability). If the toxicity rate of the currently used dose level is far smaller than pT, the mTPI will recommend escalating the dose level; if it is close to target probability (pT), the mTPI will recommend continuing at the current dose; if it is far greater than pT, the mTPI will recommend de-escalating the dose level.

Decision rules are based on calculating unit probability mass (UPM) of three dosing intervals corresponding to under, proper, and over dosing in terms of toxicity. Specifically, the under dosing interval is defined as  $(0; pT-e_1)$ , the over-dosing interval  $(pT+e_2;1)$ , and the proper-dosing interval  $(pT-e_1, pT+e_2)$ , where  $e_1$  and  $e_2$  are small fractions. Based on the safety profile of PF-04518600 as a single-agent in Study B0601002, both  $e_1$  and  $e_2$  are selected as 0.05. Therefore, the target interval for the DLT rate is (0.20, 0.30).

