# 9.2.1.2. Part B Combination Therapy

The dose escalation scheme based on mTPI method described in Section 9.2.1.1 will also be used in Part B Combination Therapy.

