# 9.2.2.2. Part B Combination Therapy

The estimated MTD is the highest tested dose combination level with mean DLT rate ≤0.25 in at least 9 DLT evaluable patients. It is also assumed that at the estimated MTD the toxicity of PF-04518600/utomilumab combination follows the monotonicity assumption that a higher dose level of either PF-04518600 or utomilumab will result in a higher toxicity rates.

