5. ANALYSIS SETS

5.1. Full Analysis Set

The Full Analysis Set (FAS) is defined as all enrolled patients who receive at least one full or partial IV infusion of study drug PF-04518600.

5.2. 'PER PROTOCOL' Analysis Set evaluable for MTD

The per protocol analysis set includes all enrolled patients who receive at least two cycles of study medication and who do not have major treatment deviations during first two cycles.

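### Part B evaluability for the MTD is judged on PF-04518600 alone, so a patient with a utomilumab-attributed DLT can be dropped and replaced; SAP 5.2 widens the gap

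*Protocol*

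**What the plan says.** Protocol 9.1c gives one MTD-evaluable definition for the whole study. It lists two major treatment deviations: "Administration of less than 75% of the planned dose of PF-04518600 provided that the reduction is not due to toxicity attributable to PF-04518600" and "Administration of more than 150% of the planned dose of PF-04518600". Patients with such deviations "are not evaluable for the MTD assessment and will be replaced as needed to permit MTD estimation". Utomilumab appears in neither criterion nor in the exemption.

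Part B relies on that evaluable set for a two-drug question. Protocol 9.2.2.2 states: "The estimated MTD is the highest tested dose combination level with mean DLT rate ≤0.25 in at least 9 DLT evaluable patients". Protocol 9.2.1.2 carries the Part A mTPI scheme over to the combination.

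By default utomilumab is infused first and PF-04518600 at least 30 minutes later (Protocol 5.4.3). Protocol 5.4.5.6.2 adds: "If infusion related reactions are observed following the administration of the first agent, administration of the second agent will be withheld until symptoms resolve". Appendix 4 discontinues study treatment after a Grade 3 or 4 hypersensitivity reaction.

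SAP 5.2 defines the set differently. It requires at least two cycles of study drug and patients "who do not have major treatment deviations during first two cycles". It gives no dose threshold for either agent and no exemption for toxicity. SAP 5.6 and Appendix 1.2 leave the deviations to be defined later.

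**The concern.** An MTD for a combination should count every qualifying toxicity of the combination. Here the rule for who enters the denominator looks at one drug and exempts toxicity of that drug only. If the other drug causes the toxicity that stops dosing, the patient may leave the numerator and the denominator together, and a replacement comes in. The loss then depends on the outcome being estimated, so it can bias the DLT rate in one direction only: downward. With two to four patients per initial cohort and nine needed for an MTD, a single such patient can change a decision.

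**Working it through.** **Step 1: follow one patient through the text.** Suppose a Part B1 patient has a Grade 3 or 4 reaction to utomilumab on Cycle 1 Day 1, before PF-04518600 is started, and treatment is discontinued under Appendix 4.

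- PF-04518600 received: 0 of 1 planned infusions in the first cycle, or 0 of 2 in the 28-day window. Both are 0%, below 75%. (9.1c refers to the first cycle in one sentence and to the DLT observation period in the next; the result is the same.)
- Cause: the patient had not yet received PF-04518600, so the toxicity cannot be attributed to it. The exemption does not apply.
- Protocol 9.1c: not evaluable, replaced.
- Protocol 3.2: clinically significant Grade 3 or higher cytokine release, infusion and allergic reactions in the first 28 days are DLTs, with no condition on which agent caused them.
- Protocol 3.1.5.1, applied to Part B by 3.1.5.2: replacement is for withdrawal before Day 28 for reasons other than investigational product toxicity. That wording covers both agents, so this patient would not be replaced.
- SAP 5.2: fewer than two cycles received, so excluded. The same holds for any patient stopped before two cycles by a DLT, whichever agent caused it.
- SAP 5.1 and 5.3: the full and safety sets require at least part of a PF-04518600 infusion, so this patient falls outside those too.

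**Step 2: effect of one dropped DLT on the plan's rules.** Replace one DLT patient by one without a DLT. The decisions are read from Protocol Table 3:

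- n = 3: 1/3 is Stay; 0/3 is Escalate. The same change occurs at n = 4 and 5.
- n = 6: 2/6 is Stay; 1/6 is Escalate. The same change occurs at n = 7 to 12.
- n = 9: 3/9 and 2/9 are both Stay, so escalation is unchanged. The MTD rule does change: 3/9 = 0.333 > 0.25 fails; 2/9 = 0.222 ≤ 0.25 passes.

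As a check, Table 3 was rebuilt from the stated Beta(0.75, 0.65) prior, target 0.25 and half-widths 0.05, with an assumed 0.95 cut-off for unacceptable toxicity. It matched 64 of 72 filled cells, including 0/3, 1/3, 1/6, 2/6, 2/9 and 3/9.

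**Step 3: illustration over repeated trials.** The documents give no rates, so these are assumptions: true DLT probability p = 0.35, and a fraction s of DLT patients dropped and replaced. The DLT probability among retained patients is p′ = p(1 − s)/(1 − ps). The chance of passing with nine patients is the binomial probability of at most 2 DLTs.

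- s = 0: p′ = 0.350, chance 0.34
- s = 0.10: p′ = 0.315/0.965 = 0.326, chance 0.39
- s = 0.25: p′ = 0.2625/0.9125 = 0.288, chance 0.50
- s = 0.50: p′ = 0.175/0.825 = 0.212, chance 0.71

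**Step 4: the secondary gap.** Utomilumab is given once in the 28-day window. If k of nine evaluable patients were under-dosed with it and had an assumed DLT risk of 0.10 (the rest 0.35), the chance of at most 2/9 rises from 0.34 to 0.40, 0.47 or 0.55 for k = 1, 2 or 3. The direction follows from the monotonicity assumption in Protocol 9.2.2.2.

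**The case against.** Much of the plan points the other way. The DLT definition and the replacement rule in 3.1.5.1 are agent-neutral. The mTPI algorithm is said to use all patients treated at a dose level. Protocol 9.6.1 and SAP 7.2.1 speak of DLTs observed in the dosing cohorts. Part B relatedness is recorded against the combination. Protocol 3.3 sets a separate MTD limit for Grade 3 and 4 cytokine release, infusion and allergic reactions. The deviation list in 9.1c is open-ended, and SAP 5.6.2 foresees a review before database closure.

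This stands to the extent that 9.1c is one literal reading in conflict with other sections, not a settled rule. It does not remove the conflict. Nothing says which section prevails, and the SAP, which states that it supersedes the protocol's statistical considerations, excludes such patients more widely. SAP 7.2.1 uses the full analysis set, which itself requires PF-04518600 exposure. The limits in 3.3 are partial: one Grade 3 event in nine patients would not trigger them.

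Two stronger readings are tempting and not supported:

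- A reader might infer that every utomilumab infusion reaction removes a patient. Withholding the second agent until symptoms resolve is a delay, and after a Grade 2 reaction Appendix 4 resumes at half the rate, which is not a lower dose. The path matters mainly for Grade 3 or 4 reactions that stop treatment.
- A reader might infer that patients whose utomilumab is stopped for toxicity carry on with PF-04518600 and count as evaluable. Protocol 5.4.5.6.2 requires both agents to be interrupted or discontinued together, so the secondary gap is confined to under-dosing for other reasons.

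**Conclusion.** The point holds as a defect in the analysis-set definition and as a contradiction between Protocol 9.1c and Protocol 3.1.5.1 and 3.2, which SAP 5.2 widens. One dropped DLT is enough to turn Stay into Escalate at small cohort sizes, or to let a level with 3/9 pass as 2/9.

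The size in this trial is unknown. The 3/9 example and the probabilities in the working are illustrations on assumed rates. The visible text contains no B1 DLT data; it reports no DLTs in 52 Part A1 patients or in the cited utomilumab studies. A reader might infer that the B1 MTD or the B2 dose is wrong, or that particular B1 patients were misclassified. The documents support neither. The B2 dose is already selected (Protocol 3.1.2.2), so what remains at stake is how the B1 evaluable set, DLT rate and MTD are reported.

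**What to change.** - Reconcile Protocol 9.1c with 3.1.5.1, 3.2 and SAP 5.2, and say which definition governs.
- In 9.1c, for Part B, apply the under- and over-dosing limits to each agent, and extend the exemption to toxicity attributable to either investigational product.
- In both 9.1c and SAP 5.2, state that a patient with a DLT in the observation period is always MTD-evaluable, whatever amount of either agent was given. The two-cycle requirement then applies only to patients without a DLT.
- In the same edit, decide whether the SAP 5.1 and 5.3 sets should admit a Part B patient who received only utomilumab.
- In the study report, list every B1 patient excluded from the MTD set, with the reason and DLT status.

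The cost is a few sentences while the SAP's deviation definitions are still open, plus a check of B1 patients against the revised definition. The number reclassified cannot be predicted from the documents. Treatment, data collection and sample size do not change.
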